### **10.3 Study Procedure Discontinuation/Termination**

All subjects are free to withdraw from participation in this study at any time, for any reason, specified and unspecified, and without prejudice. The reason for the subject discontinuing study treatment or terminating from the study will be recorded on the Source Documents (SD) and eCRF.

Reasons for study termination include:

1. Development of an AE that interferes with the subject's continued participation.
2. Subject refuses further treatment and/or follow-up and withdraws consent.
3. After receiving platelet count based on the venous sample, a subject qualifies for a study procedure which has already reached its target enrollment (ie, testing indicates the subject qualifies for single platelet donation; however, 93 subjects have already completed the single platelet product donation).

4. Investigator decision.
5. Sponsor decision.
6. Subject is lost to follow-up.
7. Subject death.

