### **15.2.2 Secondary Endpoint**

The secondary endpoint of platelet yield will be summarized for single, double, and triple platelet products. Separately for single, double, and triple platelet products, the lower one-sided 95% exact binomial confidence intervals will be calculated for the proportion of platelet units with an acceptable platelet yield. If 16 or fewer failures are observed, then the confidence interval will suggest that the true success rate is at least 75% with 95% confidence for the given platelet product.

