3.1 Sample Size

As specified in the FDA guidance, for up to 1 allowed failure, 93 platelet products are required to show that the proportion of platelet units with an acceptable residual WBC level is at least 95% with 95% confidence. With 93 platelet products being collected, 16 failures or less is required to show that the proportion of platelet units with an acceptable platelet yield is at least 75% with 95% confidence.

Up to 450 healthy adult subjects will be enrolled in this study to complete 279 procedures (93 single, 93 double, and 93 triple platelet products).

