3.2 Study Populations

Analysis populations for this clinical investigation will be the Full Analysis Set (FAS) and Safety Populations.

For all analyses by platelet product, the platelet product type (single, double, triple, or unassigned) will be determined from the calculated platelet yield (see Section 3.3) using the following.

- If the platelet yield, rounded to the nearest tenth, is $\geq 9.3 \times 10^{11}$, then the product will be analyzed as a triple.
- Otherwise, if the platelet yield, rounded to the nearest tenth, is $\geq 6.2 \times 10^{11}$, then the product will be analyzed as a double.
- Otherwise, if the platelet yield, rounded to the nearest tenth, is $< 6.2 \times 10^{11}$, then the product will be analyzed as a single.
- Otherwise, if the procedure was not started, not completed or the platelet yield could not be determined for some other reason, as per the protocol analysis exclusion criteria, then the subject will be analyzed as “Unassigned”.

The Safety Population will include all subjects enrolled in this trial for whom at least 1 apheresis procedure is initiated. A procedure will be considered to have been initiated if a Trima procedure start date and time are present. The Safety Population will be used for all summaries except the primary and secondary endpoints and the derived apheresis related parameters.

Due to the design of the study, a given subject may be enrolled in the study on multiple occasions. These subjects may also qualify for the Safety Population more than once. If this occurs, the subjects will be analyzed separately for each enrollment.

The Full Analysis Set (FAS) will be defined separately for single, double, and triple platelet products and will not include any repeat subjects. The FAS for a given platelet product will consist of all collections that do not meet any of the exclusion criteria specified below. The FAS will be used to examine the primary and secondary endpoints and the derived apheresis related parameters.

Data points will be excluded from the FAS analysis in the following situations:

1. Inability to collect a complete unit due to:
 - a. Subject issues (inadequate access, reaction, needle abort, procedure disqualification upon Trima Accel device update of subject platelet count and hemoglobin or hematocrit).
 - b. Decision to stop procedure by subject, Investigator, nursing staff or operator.

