3.4 Primary Endpoints

- Proportion of platelet units with an acceptable residual WBC level for single platelet products.
- Proportion of platelet units with an acceptable residual WBC level for double platelet products.
- Proportion of platelet units with an acceptable residual WBC level for triple platelet products.

The acceptable residual WBC level is defined as following:

For single platelet products: residual white blood cell measurement, rounded to the nearest tenth, $< 5.0 \times 10^6$.

For double platelet products:

- Parent container has a residual white blood cell measurement, rounded to the nearest tenth, $< 8.0 \times 10^6$,
- If not met, each component residual white blood cell measurement, rounded to the nearest tenth, $< 5.0 \times 10^6$.

For triple platelet products:

- Parent container has a residual white blood cell measurement, rounded to the nearest tenth, $< 12.0 \times 10^6$,
- If not met, each component residual white blood cell measurement, rounded to the nearest tenth, $< 5.0 \times 10^6$.

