3.7.3 Efficiency Analysis

Primary Endpoints

Primary Endpoint Acceptance Criteria

| Parameter | Measured | Acceptance Criteria |
|----------------------------------|--|--|
| Residual WBC Count – Single Unit | Flow cytometry; BD Leukocount™ or equivalent | Residual WBC count is $< 5.0 \times 10^6$ |
| Residual WBC Count – Double Unit | Flow cytometry; BD Leukocount or equivalent | Residual WBC count is $< 8.0 \times 10^6$ or each component $< 5.0 \times 10^6$ |
| Residual WBC Count – Triple Unit | Flow cytometry; BD Leukocount or equivalent | Residual WBC count is $< 12.0 \times 10^6$ or each component $< 5.0 \times 10^6$ |

Abbreviations: WBC = white blood cell.

Summary statistics will be provided separately for single, double, and triple residual WBC levels. The summaries will include N, mean, standard deviation, median, minimum, and maximum.

Frequencies and percentages of platelet units with an acceptable residual WBC level and the lower one-sided 95% exact binomial confidence intervals (Clopper-Pearson) will be calculated separately for single, double, and triple platelet products. If the lower one-sided confidence interval is greater than 95%, then it will be concluded that the

proportion of platelet units with an acceptable residual WBC level is at least 95% for the given platelet product.

Secondary Endpoints

Secondary Endpoint Acceptance Criteria

| Parameter | Measured | Acceptance Criteria ^a |
|------------------------------|---------------------------------|---|
| Platelet yield – Single Unit | Platelet concentration × volume | Platelet yield is $\geq 3.0 \times 10^{11}$ |
| Platelet yield – Double Unit | Platelet concentration × volume | Platelet yield is $\geq 6.2 \times 10^{11}$ |
| Platelet yield – Triple Unit | Platelet concentration × volume | Platelet yield is $\geq 9.3 \times 10^{11}$ |

^a These yields represent typical lab minimums for splitting into double and triple platelet products.

Platelet yield will be summarized separately for single, double, and triple platelet products. The summaries will include N, mean, standard deviation, median, minimum, and maximum.

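### Enrolment closes by the product a donor qualifies for, but the primary WBC analysis groups products by achieved yield, so a group (most likely triples) may end below 93, where no failure is allowed

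*SAP*

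**What the plan says.** **Closing a stratum.** Protocol 10.3, reason 3, ends participation when, on the venous platelet count, "a subject qualifies for a study procedure which has already reached its target enrollment". Its example is a donor who qualifies for a single once 93 singles have been completed. Protocol 15.4 item 2 and SAP 3.2 exclusion 2 repeat the rule. The decision is taken before that donor's product has a yield.

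**Analysing a stratum.** SAP 3.2 states: "For all analyses by platelet product, the platelet product type (single, double, triple, or unassigned) will be determined from the calculated platelet yield". A rounded yield of at least 9.3×10^11 makes a triple, otherwise at least 6.2×10^11 makes a double, and anything lower is a single.

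**The WBC limit follows the type** (SAP 3.4). "For single platelet products: residual white blood cell measurement, rounded to the nearest tenth", must be below 5.0×10^6, with no component route. Doubles pass with a parent container below 8.0×10^6 and triples below 12.0×10^6. Failing that, they pass if every component is below 5.0×10^6.

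**Size and decision rule.** SAP 3.1 gives the size for a 95% target as follows: "for up to 1 allowed failure, 93 platelet products are required to show that the proportion of platelet units with an acceptable residual WBC level". The same section plans "to complete 279 procedures (93 single, 93 double, and 93 triple platelet products"). SAP 3.7.3 says "the lower one-sided 95% exact binomial confidence intervals (Clopper-Pearson) will be calculated separately for single, double, and triple platelet products", and declares success on this condition: "If the lower one-sided confidence interval is greater than 95" (per cent).

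**Two related differences.** The FAS is the first 93 eligible collections per type in protocol 15.3, but all eligible collections in SAP 3.2. The enrolment ceiling is 350 in the protocol (8.1, 9.1) and 450 in SAP 3.1.

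**The concern.** The count that closes enrolment and the count that enters the primary analysis appear to use different meanings of single, double and triple. A product collected as a triple with a rounded yield below 9.3×10^11 leaves the triple group. A product collected as a double below 6.2×10^11 becomes a single. Triples are the most exposed: they can lose products downward, and gain only when a smaller collection happens to reach 9.3×10^11.

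Two things are at stake. One is the single WBC failure that the design allows per type, which depends on the group reaching 93. The other is which WBC limit a re-sorted product has to meet.

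**Working it through.** **1. Reproduce the 93.** Inputs (SAP 3.1, 3.7.3): reference rate 0.95, one-sided 5%, Clopper-Pearson. With f failures in n, the lower limit is the 5% quantile of Beta(n−f, f+1). It exceeds 0.95 exactly when the probability of at most f failures, at a true success rate of 0.95, is below 0.05.

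- n=93, f=1: 0.95^93 + 93×0.05×0.95^92 = 0.04998; lower limit 0.950006. Passes.
- n=92, f=1: the same sum is 0.0521; lower limit 0.94947. Fails.
- Smallest n for 0, 1, 2 and 3 failures: 59, 93, 124 and 153.

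The plan's 93 is right and has no slack. Groups of 59–92 allow no failure, 93–123 allow one and 124–152 allow two. Below 59, no result can pass.

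**2. What type means in the protocol.** Protocol 15.2.2 says: "If 16 or fewer failures are observed, then the confidence interval will suggest that the true success rate is at least 75" (per cent). At n=93 the lower limit is 0.7505 with 16 failures and 0.7385 with 17, so this figure also reproduces. A double or triple can miss its yield limit only if it is still called a double or triple when its yield is short. The protocol's type is therefore the product collected. Under SAP 3.2 no analysed double or triple can miss its yield limit. The SAP changed the definition and kept the protocol's numbers.

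**3. Chance of passing for one group.** The true WBC success rate p is an assumption. At n=93 the chance is p^93 + 93(1−p)p^92; at n=92 it is p^92.

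| Assumed p | n=93, at most 1 failure | n=92, no failure |
|---|---|---|
| 99% | 76.2% | 39.7% |
| 99.5% | 92.1% | 63.1% |
| 99.9% | 99.6% | 91.2% |

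The drop is largest just under 93. At n=77 the chance at 99% is 46.1%, because fewer products have to be clean.

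**4. How easily a group falls short.** The downgrade rate q is not in the documents. If exactly 93 triples are collected and none move up, the chance that all stay triples is (1−q)^93: 39% at q=1%, 15% at 2%, 0.9% at 5%. Suppose instead 93 of each are collected and k triples and k doubles each drop one class:

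| k | Triples / doubles / singles | Failures allowed |
|---|---|---|
| 1 | 92 / 93 / 94 | 0 / 1 / 1 |
| 5 | 88 / 93 / 98 | 0 / 1 / 1 |
| 16 | 77 / 93 / 109 | 0 / 1 / 1 |

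The last row takes the most yield failures that the secondary criterion tolerates. It is an extreme, not a forecast.

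**5. The WBC limit that a re-sorted product meets.** These effects do not depend on group size.

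- Collected as a double, yield 6.0×10^11, parent WBC 6.0×10^6: passes as a double (below 8.0) but is a failure among singles (not below 5.0).
- Collected as a triple, re-sorted to a double, parent WBC 8.0–11.9×10^6: passes only by the component route.
- Collected as a double, yield 9.4×10^11, parent WBC 10.0–11.9×10^6: passes under the triple limit of 12.0. Two equal units would each hold about 5.0–6.0×10^6; three would each hold about 3.3–4.0×10^6.

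**The case against.** A reader might infer that the analysed groups are bound to miss 93, that the one-failure allowance is lost across the design, or that the error rate is compromised. The documents support none of these.

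- **Not a certainty.** No downgrade rate is given. The SAP's FAS takes all eligible collections, and its ceiling of 450 leaves room for more. Laboratory tests are run locally (protocol 11), so a yield-based count is feasible, and no section expressly rules one out. This stands, but no section directs anyone to use that room, SAP 3.1 still plans 279 procedures, and the protocol's yield allowance in 15.2.2 implies that its count is by product collected.
- **Not the whole design.** Singles would usually gain products, and one failure in 109 still gives a lower limit of 95.7%. Doubles can move either way. This stands.
- **Validity is intact.** The SAP applies the exact bound at whatever size results, so the one-sided error stays at or below 5%. This stands.
- **The drop may be smaller.** Protocol 5.1 reports no WBC failures in early standard-product series of 36 and 30. If the true rate is near 99.9%, the loss is from 99.6% to 91.2%. This is fair, which is why the range is shown.
- **Yield-based limits are defensible.** The footnote to protocol Table 7-2 describes the yields as usual laboratory minimums for splitting. A product with yield 6.0×10^11 and WBC 6.0×10^6 might then stay one transfusable unit, above the objective of 5.0×10^6 per unit. This stands, and it argues against simply replacing the yield-based type with the targeted product.

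**Conclusion.** The point holds as an unreconciled definition that puts a group's one-failure allowance at risk. Stopping follows the product a donor qualifies for, the primary analysis follows achieved yield, and nothing connects the two or tops up a short group. The likeliest casualty is the triple group. A net loss of one product from 93 removes its allowance and lowers its chance of passing by about 36 percentage points at an assumed true rate of 99%, 29 at 99.5% and 8 at 99.9%. A second effect, at any group size, is that some products are judged against a different WBC limit from that of the product collected.

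This rests on assumed WBC success rates, an unknown downgrade rate, and reading the protocol's count as one of products collected. The harm is to the chance of passing and to which limit applies, not to the validity of the bound.

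**What to change.** Use one definition of product type for both stopping enrolment and the primary analysis.

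1. If the yield-based type is kept, reword protocol 10.3 reason 3, protocol 15.4 item 2 and SAP 3.2 exclusion 2 so that a stratum closes only when 93 evaluable products of that calculated type exist. This restores n=93 with one failure allowed.
2. Reconcile the FAS (first 93 in the protocol, all eligible collections in the SAP) and the enrolment ceiling (350 or 450).
3. Add a supportive table of the primary result by targeted product, each judged against that product's limit. This needs the target to be among the Trima procedure details recorded under protocol 10.2.2, whose contents are not listed.

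**Cost.** Yields have to be calculated and counted as collections accrue. Some extra collections may be needed within the ceiling: the expected number of triple procedures is 93/(1−q), which is about 98 at an assumed downgrade rate of 5% and 113 at 17.2% (16/93). The rest is wording and one table.

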# **8 INVESTIGATIONAL PLAN**

## **8.1 Study Design**

This is a prospective, open-label, multi-center controlled study to evaluate the leukoreduction of platelets stored in 100% plasma collected on the Trima Accel system with Version 7.0 software enhancements. Up to 350 healthy adult subjects will be enrolled in this study to ensure 93 single, 93 double, and 93 triple platelet product evaluable data points. Evaluable is defined as a completed platelet product that does not meet any of the protocol analysis exclusion criteria (Section 15.4).

The additional subjects account for screen failures, incomplete procedures, and protocol analysis exclusions.

Concurrent plasma will be collected from qualifying subjects to exercise the platelet/plasma product combination. Of the 93 evaluable procedures required for each type (singles, doubles, and triples) at least 25% of collections will include concurrent plasma collection. The Trima Accel system calculates subject eligibility for blood product combinations based on platelet count, hemoglobin or hematocrit, and total blood volume (TBV) of the subject.

Red blood cells will not be collected in this study; platelets will be collected in 100% plasma. The Trima Accel system collects RBCs after platelets and plasma, therefore there is no effect of RBC collections on the platelet collections due to platelet collection software modifications. Similarly, there is no effect of the platelet collections on subsequent RBC collections.

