### **9.4 Enrollment**

A donor is considered to be an enrolled subject following informed consent. It is expected that, due to the screening and eligibility requirements, some fraction of subjects will not qualify for a platelet/plasma donation after consent and some who are enrolled may not complete their anticipated procedures. Subjects will be considered screen failures if they fail to meet any of the eligibility criteria, and subjects who do not complete their anticipated procedure (after venipuncture) will be considered as an early termination.

After informed consent has been obtained, subjects will receive a unique study identification number (USID). The USID number will use the following convention: 60XX-YYY, where XX is the pre-assigned site number and -YYY will be a sequential number starting with 001. The USID number will be recorded on the electronic Case Report Form (eCRF).

Subjects that fail screening criteria on information or laboratory values that are anticipated to change, may be rescreened. Subjects that have incomplete procedures or donated a product that meets any of the protocol analysis exclusions (Section 15.4) may rescreen if they meet all

inclusion criteria when they return. Subjects that are rescreened will be assigned a new USID number.

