## **15.3 Analysis Populations**

The safety population will include of all subjects enrolled in this trial for whom at least 1 apheresis procedure is initiated. The Full Analysis Set (FAS) will be defined separately for single, double, and triple platelet products. The FAS for a given platelet product will consist of the first 93 collections that do not meet any of the protocol exclusion criteria described in Section 15.4. The FAS will be used to examine the primary and secondary endpoints.

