 - c. Equipment failure or malfunction (unrecoverable system failure; plugged or malfunctioning filter[s]).
 - d. Protocol deviation.

2. Decision to stop the procedure due to a change in the subject platelet count (i.e. subject qualifies for double, however day-of platelet count is for a single platelet product and 93 single platelet products have already been collected).
3. Failure or inability to update the Trima Accel system with the actual platelet count (platelet count performed on sample taken from Trima Disposable sample pouch) AND the actual platelet count differs from the entered platelet count by more than 10%. Updating the Trima Accel system with actual platelet count from the sample pouch is standard procedure for the Trima Accel system.
4. Incomplete or incorrect collection procedure or post-collection processing due to:
 - a. Equipment failure or malfunction.
 - b. Subject issues (inadequate access, reaction, needle abort).
 - c. Unanticipated centrifuge stop during collection procedure.
 - d. Failure to follow post-collection handling procedure outlined in the Trima Operator's Manual, and supplement(s).
 - e. Subject and procedure samples are not taken as specified in protocol.
 - f. Incorrect solution added to platelets prior to storage (eg platelet additive solution).
 - g. Results of endpoint assays are not available.

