3.3 Apheresis Related Parameter Calculations

Parent container:

$$\text{Platelet Volume (mL)} = \frac{\text{Dual Bag Platelet Plus Product Weight (g)} - \text{Dual Bag Tare Weight(g)}}{1.03 \left(\frac{\text{g}}{\text{mL}}\right)}$$

$$\text{Plasma Volume (mL)} = \frac{\text{Plasma Bag Weight (g)} - \text{Plasma Bag Tare Weight(g)}}{1.03 \left(\frac{\text{g}}{\text{mL}}\right)}$$

$$\text{Average Platelet Concentration (x10}^3/\mu\text{L)} = \frac{1^{\text{st}} \text{ CBC (x10}^3/\mu\text{L)} + 2^{\text{nd}} \text{ CBC (x10}^3/\mu\text{L)}}{2}$$

$$\text{Platelet Yield (x10}^{11}\text{)} = \frac{[\text{Average Platelet Concentration}] * [\text{Dilution Factor}] * [\text{Platelet Volume}]}{100,000}$$

$$\text{Residual WBC Count (x10}^6\text{)} = \frac{[\text{Raw WBC Count (cells}/\mu\text{L)}] * [\text{Platelet Volume}]}{1,000}$$

Individual components (Products A, B, and C, where applicable, from the eCRFs):

$$\text{Platelet Volume (mL)} = \frac{\text{Bag Platelet Plus Product Weight (g)} - \text{Bag Tare Weight(g)}}{1.03 \left(\frac{\text{g}}{\text{mL}}\right)}$$

$$\text{Residual WBC Count (x10}^6\text{)} = \frac{[\text{Raw WBC Count (cells}/\mu\text{L)}] * [\text{Platelet Volume}]}{1,000}$$

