3.7 Statistical Analysis

All data collected on the eCRFs will be presented in the listings. Missing data will not be imputed. All analyses will be based on observed data only.

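### Exclusion 4g, as worded, can remove a double or triple whose parent container is at or above its WBC limit when a component result is missing, even if failure is already determined

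*SAP*

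**What the plan says.** SAP 3.4 scores doubles and triples in two steps. The parent container is compared with 8.0 x 10^6 (double) or 12.0 x 10^6 (triple). The second step is conditional: "If not met, each component residual white blood cell measurement, rounded to the nearest tenth" must be below 5.0 x 10^6.

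Item 4g in SAP 3.2, worded the same in Protocol 15.4, takes a product out of the analysis when "Results of endpoint assays are not available". It does not say whether component counts are endpoint assays, and it makes no exception for a parent that is over its limit.

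On missing data, SAP 3.7 says: "Missing data will not be imputed. All analyses will be based on observed data only". Component formulas in SAP 3.3 come under the label "Individual components (Products A, B, and C, where applicable, from the eCRFs". Neither document says that components must be assayed when the parent exceeds its limit.

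Excluded products can be replaced. The protocol FAS (15.3) is the "first 93 collections that do not meet any of the protocol exclusion criteria described in Section 15.4". Protocol 8.1 provides for this in the enrolment total: "The additional subjects account for screen failures, incomplete procedures, and protocol analysis exclusions". Under Protocol 9.4, a donor who "donated a product that meets any of the protocol analysis exclusions (Section 15.4) may rescreen". The SAP defines the set differently ("The FAS for a given platelet product will consist of all collections that do not meet any of the exclusion criteria specified below"), but still plans to complete 93 of each type.

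**The concern.** The same missing result is treated differently depending on the parent count. A double with a parent of 3 x 10^6 and no component result is acceptable at step one and stays in. A double with a parent at or above 8.0 x 10^6 and no component result can leave the FAS under 4g. By this route, every product lost comes from the only group of doubles or triples that can fail, so the missingness is related to the outcome.

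Read literally, 4g also reaches products whose failure is already known. One example is a double with one component measured at or above 5.0 x 10^6 and the other missing. Another is a parent count too high for all components to pass.

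The success rule allows a single failure per product type, so the handling of one product can decide a primary conclusion. Two analysts could read 4g differently and reach opposite conclusions from the same data.

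**Working it through.** **Inputs.** From SAP 3.1 and 3.7.3: 93 products per type, at most 1 failure, one-sided 95% Clopper-Pearson lower limit, required to exceed 95%. From SAP 3.4: parent limits 8.0 and 12.0, component limit 5.0 (all x 10^6, rounded to one decimal). The share of failing products lost to missing component results is not in the documents and is assumed, with a range shown.

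**1. The plan's own figure.** With f failures in n, the lower limit L(n, f) is the 5th percentile of Beta(n - f, f + 1).
- L(93, 1) = 95.0006% and L(92, 1) = 94.95%, so 93 is the smallest n with one failure. The stated design reproduces.
- Chance of passing at a true 95%: 0.95^93 + 93 x 0.05 x 0.95^92 = 0.0085 + 0.0415 = 0.0500.

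**2. Which products are affected.** A component rounds below 5.0 only if it is below 4.95. If all components pass, the parent total is below 2 x 4.95 = 9.90 (double) or 3 x 4.95 = 14.85 (triple), measurement error aside.

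| Parent, double | Parent, triple | Outcome if no component result exists |
|---|---|---|
| below 8.0 | below 12.0 | Acceptable; components not needed |
| about 8.0-9.8 | about 12.0-14.8 | Undetermined; a double at 9.0 split evenly gives 4.5 and 4.5 and passes |
| about 9.9 or more | about 14.9 or more | At least one component must fail |

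An over-limit parent with any one component known to be at or above 5.0 is also a determined failure, whatever the missing result would have been.

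**3. Effect on the decision.**
- L(93, 2) = 93.38%: not met.
- One of the two failures excluded and replaced by a success: L(93, 1) = 95.0006%: met.
- One of the two excluded without replacement: L(92, 1) = 94.95%: not met. The reversal therefore needs the replacement that Protocol 8.1, 9.4 and 15.3 provide.
- With both failures counted, 124 products would be needed: L(124, 2) = 95.01%, against L(123, 2) = 94.97%.

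**4. Effect on the false-pass chance.** Let q be the true failure rate and m the share of failing products excluded and replaced. The failure rate among evaluable products is q(1 - m)/(1 - qm), and a pass needs at most 1 failure in 93. At q = 0.05:

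| m (assumed) | Failure rate among evaluable products | Chance of a pass |
|---|---|---|
| 0% | 0.0500 | 5.0% |
| 5% | 0.0475/0.9975 = 0.0476 | 6.0% |
| 10% | 0.0450/0.9950 = 0.0452 | 7.3% |
| 20% | 0.0400/0.9900 = 0.0404 | 10.6% |
| 50% | 0.0250/0.9750 = 0.0256 | 30.8% |

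This models the loss of true failures only. Undetermined products that would have passed could also be lost, which would offset part of the effect.

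**The case against.** Item 4g can be read so that the problem does not arise. It sits under a stem about incomplete or incorrect collection or post-collection processing. Protocol 10.2.3 lists one residual WBC count for the platelet product and no separate component assay. With a parent count on file, an endpoint result is arguably available. A product that meets neither step of SAP 3.4 would then simply be not acceptable. This reading is possible, but neither document states it, and the plain wording of 4g acts earlier, by removing the product from the FAS.

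The harm also needs several things together: an over-limit parent, a missing component result, the exclusion reading, replacement and a borderline failure count. Protocol 5.1 and 5.2 report earlier results of 36/36, 30/30 and 30/30 below 5.0 x 10^6 per dose. All eCRF data will be listed, and missing data must be explained (SAP 3.7, Protocol 16.4.2), so recorded over-limit parents would be visible. These points stand and lower the priority. They do not settle which rule the primary analysis follows.

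Three stronger readings are tempting, and the documents do not support them:
- **A parent over its limit has already failed.** The criterion allows success through the components, and parents of about 8.0-9.8 or 12.0-14.8 are undetermined.
- **4g can only raise the success rate.** It also covers singles, missing parent counts and missing yield assays, whatever the WBC outcome. Dropping an undetermined product that would have passed can lower the rate.
- **A missing platelet count improperly removes a known WBC result.** SAP 3.2 assigns product type from the calculated yield and labels a product without one as unassigned. There is then no product-specific analysis set, and no WBC limit, to apply to it.

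**Conclusion.** The concern holds as a gap in a stated rule. As worded, 4g can remove doubles and triples selectively, by an outcome-related route, and this includes products whose failure is already determined. One true failure excluded and replaced moves a product type from 93.38% (not met) to 95.0006% (met). The rise in the false-pass chance from 5.0% to 7.3% or 10.6% rests on an assumed 10% or 20% loss of failures. The documents give no rate of over-limit parents or of missing component results, so they show that this can happen and not that it will. Singles are not affected by the two-step route. Because it depends on one of two readings and on an unknown frequency, it is a cheap improvement worth making before analysis, not an essential correction.

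**What to change.** Amend 4g in SAP 3.2 and Protocol 15.4, with a matching line in SAP 3.7:

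1. A double or triple with an available parent count at or above its limit, and without component results showing every component below 5.0 x 10^6, stays in the FAS and counts as not acceptable for the primary endpoint.
2. For WBC results, 4g applies only when there is no parent count and no component results that determine the outcome.
3. SAP 3.7 states that item 1 is part of the endpoint definition and not imputation, so that it does not conflict with the no-imputation rule.
4. Every 4g exclusion is listed with its parent WBC result.

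The cost is a few sentences across the two documents and one listing. The downside is that some undetermined products that would have passed are counted as failures. Sites avoid this by assaying the components whenever the parent is at or above its limit.
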